7.2 Stratification, Randomization, and Blinding/Masking

Laboratory personnel conducting the assays will be blinded to diagnostic group (non-AD, mild AD, or moderate-to-severe AD) and study therapy regimen, until after samples are processed. Analytical personnel who are unblinded for quality control purposes or to complete interim analyses of the data will not be involved in processing samples.

8 GENERAL ANALYSIS AND REPORTING CONSIDERATIONS

8.1 Analysis Visits

The Day 7 Visit – for all relevant clinical and outcome groups, the Day 7 visit pertains to the 1st Week Clinical Assessment Visit that occurs 7 days (± 3 days) after the Baseline Assessment (Day 0) at study enrollment.

The End of Study Assessment (Day 168-224) Visit – for Non-AD, Topical Steroid Responders, and Long-term Dupilumab participants, their End of Study Assessment Visit occurs 168 days (± 3 days) after the Baseline Assessment (Day 0) at study enrollment. For Topical Steroid Non-Responders, their End of Study Assessment Visit occurs 133 days (130-136 days) after Dupilumab Initiation, which can occur any time between 35 days (-3, +6 days) and 91 days (± 3 days) after the Baseline Assessment (Day 0) at study

enrollment depending on when the participant obtains the qualifying EASI score (> 7) for initiating Dupilumab. Hence, the End of Study Assessment Visit can range from Day 168 to 224.

Unscheduled Visit - participants may be asked to return to the clinic for Unscheduled Visits, as needed, to provide additional skin swabs, STS, and/or skin biopsies for studies, or if samples are lost or destroyed, or if insufficient yields were obtained at a previous study visit. Thus, for the purposes of the analyses described in this SAP, the STS samples obtained at an unscheduled visit that occurred after the Day 7 or End of Study Assessment visits may be used for analysis instead if the samples obtained at the scheduled visits were lost, destroyed, or yielded insufficient gene expression.

8.2 Stratification and covariates

Throughout analysis, our approach will be to analyze pediatric and adult populations separately to better model and discover any cohort-specific endotypes and phenotypes. We will then compare how effects of interest differ between the two age cohorts. We will also fit combined pediatric/adult models using interaction terms with age group to help identify effects that are shared and unique to age groups. In regards to skin sampling, in addition to skin tape strip (STS) samples collected from all children and adults at each sample point, we will be collecting required and optional biopsy samples from adults, depending on time point and course of treatment. We may in certain instances compare biopsy and STS samples, as information from these samples can be complementary. For AD participants, skin samples will be collected from both lesional and non-lesional skin, as applicable. Although main analyses will focus on non-lesional skin, such that signatures of AD disease and severity can specifically be tied to systemic effects on skin tissue rather than to the unique character of lesional skin, we will also investigate how AD and treatment effects differ between the two skin types.

Finally, as transcriptional responses to AD or AD treatments can also be influenced by individual traits, such as age, sex, race/ethnicity, body mass index (BMI), concomitant therapies, concomitant asthma, age of asthma diagnosis, asthma controller usage, presence and frequency of eczema herpeticum, history of Staph infection, presence of recurrent or chronic sinusitis, modified rhinitis symptom utility index (MRSUI) total score, presence and type of food and animal allergies, presence and treatment of viral/bacterial infections, smoking status and pack years of the participant or caregiver, level of compliance for the different treatments, and existence and type of adverse events, we may include these as covariates in the models below where appropriate, to ensure that such variables don't confound our inferences. Where significant, effects of these covariates on responses will be investigated by running sensitivity analyses on datasets stratified based on these covariates.

8.3 Descriptive analyses

Descriptive analyses will be reported separately by baseline AD severity group and study outcome group. Continuous baseline measures will be reported as 1) mean (or geometric mean) with standard deviation, or 2) median with 1st and 3rd quartile, as appropriate. Categorical baseline and demographic characteristics and participant disposition will be reported as frequencies and proportions.

9 ENDPOINT EVALUATION

9.1 Primary Analysis of Primary Endpoint

9.1.1 *Determining if the type 2-high non-lesional skin (skin tape) endotype is associated with current mild versus moderate-to-severe AD disease [Primary Objective]*

This analysis will utilize WTS data from the Day 7 Visit and will be performed separately for children and adults, but also in a combined analysis (described below). We will first define the type 2-high skin endotype in the transcriptome dataset by identifying a network of co-expressed genes enriched in known markers of type 2-inflammation using weighted gene co-expression analysis (Weighted Gene Co-expression Network Analysis (WGCNA); Langfelder and Horvath 2008), or similar analysis. These networks should capture distinct biological processes taking place in these participants, including type 2-high inflammation. The type 2-high network will be identified as the network with strongest enrichment of published type 2 inflammation gene sets (Dyjack et al. 2018; Leung et al. 2019), based on hypergeometric tests of over-representation. Alternatively, if a type 2 network is not well defined, we may use a known skin type 2 inflammatory gene set.

Specifically, we will test whether expression of the type 2 endotype is associated with AD and AD severity using the following 8 logistic regression models:

Regressor	Population	Response Groups	Model #
Type 2 Inflammation in Non-lesional STS collected at Day 7	Adults (18+ year olds)	Non-AD vs. DNAD (all severity) at Day 7	1
		Non-AD vs Mild DNAD at Day 7	2
		Non-AD vs Moderate-to-Severe DNAD at Day 7	3
		Mild vs. Moderate-to-Severe DNAD at Day 7	4*
	Children (6-17 year olds)	Non-AD vs. DNAD (all severity) at Day 7	5
		Non-AD vs Mild DNAD at Day 7	6
		Non-AD vs Moderate-to-Severe DNAD at Day 7	7
		Mild vs. Moderate-to-Severe DNAD at Day 7	8*

** Model # 4 and 8 will evaluate our primary estimand that will directly answer our primary objective. The remaining models will help support our primary findings.*

The 8 models will be fit twice, once treating type 2 inflammation as a dichotomous variable and the second time treating type 2 inflammation as a continuous variable (see below).

1. *Type 2 inflammation as a dichotomous variable:*

We will divide individuals into type 2-high and type 2-low expression categories by clustering all participants based on gene-level expression of all genes in the type 2 inflammation gene network. Thus, these dichotomous group assignments will emerge from the transcriptome data based on individuals' relative expression of the network of genes most enriched in known type 2 markers. We will then test whether type 2-high status (high vs. low) is associated with disease group identity (AD vs. non-AD, mild AD vs. non-AD, moderate-to-severe AD vs. non-AD, and mild AD vs. moderate-to-severe AD) using logistic regression, with type 2 high status as the predictor and disease group as

the outcome. We will also include relevant covariates, such as age, sex, race/ethnicity, and concomitant therapies as discussed above (Section 8.2).

2. *Type 2 inflammation as a continuous variable:*

We will calculate the geometric mean of expression across the type 2 inflammation gene network and then test whether this mean expression is associated with disease group identity using logistic regression, with mean expression (and covariates) as the predictor and disease group as the outcome.

Moreover, in addition to considering the categorical grouping of mild and moderate-to-severe AD disease (which is based on body-wide EASI as defined in section 6.2), we will also consider modeling for the association between continuous EASI scores and type 2 inflammation (both dichotomous and continuous as described above). Finally, in addition to using body-wide EASI to measure AD severity, we will also consider measuring sampling site-specific local AD severity based on local EASI score (sum of severity scores of the four clinical signs: Erythema, Edema, Lichenification, and Excoriation that were assessed at the target area sampling site) and target area assessment (TAA). We will test for association between these continuous local AD severity scores versus dichotomous or continuous type 2 inflammation measures.

As stated in 8.2, in addition to the models above, we will also run an additional 8 models (four participant-comparisons by two type 2 outcome measures) that test for association between type 2 outcome measures and disease group identity in pediatric and adult patients combined. These models will contain interactions terms involving disease status and age group to help identify disease effects that may differ by age group.

The age-stratified models defined above will also be repeated, including additional covariates as described in Section 8.2. If a covariate is found to be statistically significant in the model and if deemed appropriate, we will carry out sensitivity analyses by repeating analysis in participants stratified into covariate-based groups to determine whether effects qualitatively differ among stratified groups. For continuous covariates, this will require discretization. If sufficient samples are available for covariate-based groups, we may also fit a single model that includes the covariate and disease group with covariate interaction terms, enabling us to quantitatively determine whether disease effects differ by the covariate.

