Single-gene differential expression from matching set of Non-lesional AND Lesional STS collected at Day 7	Adults (18+ year olds)	Mild vs. Moderate-to-Severe DNAD at Day 7, Non-lesional vs Lesional, Interaction	17
	Children (6-17 year olds)	Mild vs. Moderate-to-Severe DNAD at Day 7, Non-lesional vs Lesional, Interaction	18
	Adults AND Children	Mild vs. Moderate-to-Severe DNAD at Day 7, Non-lesional vs Lesional, Adults vs. Children, Interactions	19
Single-gene differential expression from matching set of Non-lesional AND Lesional STS collected at End of Study (Day 168-224)	Adults (18+ year olds)	Mild vs. Moderate-to-Severe DNAD at End of Study, Non-lesional vs Lesional, Interaction	20
	Children (6-17 year olds)	Mild vs. Moderate-to-Severe DNAD at End of Study, Non-lesional vs Lesional, Interaction	21
	Adults AND Children	Mild vs. Moderate-to-Severe DNAD at End of Study, Non-lesional vs Lesional, Adults vs. Children, Interactions	22

** Models 2,3,6,7,10,11,14, and 15 will evaluate the first of our secondary estimands that will directly answer the first of our secondary objectives. The remaining models serve as supportive analyses.*

The 22 models defined above will then be repeated with additional covariates as described in Section 8.2. If a covariate is found to be statistically significant in the model and if deemed appropriate, we will carry out sensitivity analyses by repeating analysis in participants stratified into covariate-based groups to determine whether effects qualitatively differ among stratified groups. For continuous covariates, this will require discretization. If sufficient samples are available for covariate-based groups, we may also fit a single model that includes the covariate and disease group x covariate interaction terms, enabling us to quantitatively determine whether disease effects differ by the covariate.

Pathway and enrichment analyses will be performed on differentially expressed gene (DEG) sets to determine the biological mechanisms that underlie transcriptional differences.

9.2.2 Determining how gene expression in the skin (skin tape) changes with standard-of-care treatment (two timepoints) among the study outcome groups: (1) topical steroid responders, (2) dupilumab responders, (3) dupilumab non-responders, (4) non-AD, and (5) long-term dupilumab responders [SO #2]

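### The stratified check for differing effects is triggered by the covariate's own significance, which does not test effect modification; the interaction model that would is optional

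*SAP*

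**What the plan says.** SAP 9.1.1 states: "The age-stratified models defined above will also be repeated, including additional covariates as described in Section 8.2". No covariate interaction is named at this step, so a covariate that is significant in the model is one whose own coefficient is significant. The rule that follows is "If a covariate is found to be statistically significant in the model and if deemed appropriate, we will carry out sensitivity analyses", done by rerunning the analysis in covariate-based groups "to determine whether effects qualitatively differ among stratified groups".

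The interaction model comes last and is optional: "If sufficient samples are available for covariate-based groups, we may also fit a single model" containing the covariate and its interaction terms. The SAP itself describes that model as the quantitative way to see whether disease effects differ by the covariate.

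Sections 9.2.1 and 9.2.2 repeat the condition ("If a covariate is found to be statistically significant in the model and if deemed appropriate") and add, as 9.1.1 does, "For continuous covariates, this will require discretization". SAP 8.2 gives the general rule, "Where significant, effects of these covariates on responses will be investigated by running sensitivity analyses on datasets stratified based on these covariates", and protocol 13.1 has the same rule. Section 9.1.1 states no significance level for the trigger.

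Two kinds of interaction are exempt. Age-group interactions are planned without a trigger (SAP 8.2, 9.1.1, 9.2.1, 9.2.2), as are skin-type interactions in the secondary analyses (9.2.1, 9.2.2).

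**The concern.** The trigger and the purpose concern different parameters. In 9.1.1 disease group is the outcome, so a significant coefficient for sex says that sex is related to severity given type 2 status. It does not say whether the type 2 odds ratio differs between the sexes. In 9.2.1 and 9.2.2 the outcome is gene expression, and the same gap exists between a covariate's effect on expression and its modification of the disease-group or visit effect.

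A covariate can modify the effect with little average effect of its own, or predict the outcome strongly and modify nothing. The trigger tends to pass over the first kind and select the second. Apart from age group and skin type, the triggered rerun is the only committed check of whether results hold across covariates. At stake is how far a reader can rely on statements that the type 2 association is, or is not, consistent across participants.

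**Working it through.** **1. Inputs from the documents** (protocol 13.7.1 and Table 13.7.1.1). Moderate-to-severe versus mild: 160 versus 100 adults (N = 260) and 80 versus 50 children (N = 130). Type 2-high prevalence is 50%, alpha 0.05, power 80%. Stated minimum detectable odds ratios are 2.06 (adults) and 2.80 (children).

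**2. The plan's own figure.** The check uses the sample-size formula for logistic regression with a binary predictor, with predictor prevalence B = 0.5 and overall event rate P = 160/260 = 80/130 = 0.615:

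N = [z(0.975)·√(P(1−P)/B) + z(0.80)·√(P1(1−P1) + P2(1−P2)(1−B)/B)]² / [(P1−P2)²(1−B)]

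- Adults, odds ratio 2.06: P1 = 0.531 and P2 = 0.700 average to 0.615, giving N ≈ 258 against 260 planned.
- Children, odds ratio 2.80: P1 = 0.497 and P2 = 0.734, giving N ≈ 129 against 130.
- Solved the other way, the detectable odds ratios are 2.05 and 2.79, against 2.06 and 2.80 stated.

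The table reproduces, so the base model is the plan's own.

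**3. The trigger.** The documents give no operating figure for it, so it was simulated at the plan's sizes with 3,000 or more replicates per setting (Monte Carlo error at most about 1 percentage point). Assumptions not in the documents are a binary covariate Z split 50/50 and independent of type 2 status, a trigger at two-sided 0.05 without multiplicity correction, and the effect sizes shown.

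- Trigger: Wald p < 0.05 for Z in logit P(moderate-to-severe) = a + b·T2 + c·Z.
- Comparator: Wald p < 0.05 for g after adding g·T2·Z.

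The settings, with type 2 odds ratios by level of Z, were:

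- *A. Modifier with no average covariate effect*: 1.0 versus 4.24. Setting c = −½·ln 4.24 makes the odds ratio of Z 1/√4.24 = 0.49 in type 2-low and √4.24 = 2.06 in type 2-high, which cancel on the log scale.
- *B. Opposite-direction modifier with no average covariate effect*: 0.5 versus 4.
- *C. Modifier acting only in type 2-high participants*: 1.0 versus 4.24, with the odds ratio of Z equal to 1.0 in type 2-low and 4.24 in type 2-high.
- *D. No modification*: type 2 odds ratio 2.06 at both levels, Z odds ratio 2.
- *E. As D*, with Z odds ratio 3.

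| Setting | Adults: trigger opens | Adults: interaction test | Children: trigger opens | Children: interaction test |
|---|---|---|---|---|
| A | about 6% | about 78% | 5–6% | 47–50% |
| B | 5% | 98% | 5–6% | 79% |
| C | about 69% | 76–77% | about 42% | 45–47% |
| D | 74–76% | 5% | 45–48% | 5% |
| E | 99% | 4–5% | 83% | 5% |

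Ranges are the spread across repeated simulations. In setting C, requiring both the trigger and a significant interaction lowers detection to about 52% in adults and 18% in children.

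**4. Reading.** In A and B the trigger opens at about its nominal level, because the parameter it tests is essentially null. In D and E it opens often although there is nothing to find, and the interaction test stays near its nominal 5%.

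**The case against.** The strongest reply is that this is a matter of discretionary sensitivity analyses. Starred models 4 and 8, which carry the primary estimand, do not depend on the trigger, and neither does the power table. The age-group interaction, probably the most important one here, is already planned without a trigger, and so are the skin-type interactions. The SAP also names the interaction as its quantitative tool, and the condition written beside it is sufficient samples, so it can be read as not gated at all. All of this stands and limits the weight of the point. It leaves the interaction model optional, with no covariates named, and the committed analysis behind a test of another parameter.

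Several stronger readings are tempting and are not supported:

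- *That the plan is blind to effect modification.* Settings A and B are built so that the covariate's average effect is zero. A modifier that also has an average effect often passes, as setting C shows.
- *That a difference will be claimed when one stratum reaches p < 0.05 and the other does not.* The SAP states no such decision rule. It says only that strata will be compared qualitatively.
- *That some covariate will trigger by chance in more than half of models.* SAP 8.2 lists about 17 covariates, and 1 − 0.95^17 = 0.58. But 8.2 says these may be included where appropriate, so 17 simultaneous independent tests are not planned, and the extra condition that the rerun be deemed appropriate also intervenes.
- *That the figures carry over to SO1 and SO2.* Those analyses are per gene, and 9.2.1 applies Benjamini-Hochberg adjustment throughout the SAP without saying whether it covers covariate p-values used as a trigger. Nothing was computed for them.

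**Conclusion.** The point holds as a defect of selection rule. The only committed check of whether effects differ by covariates other than age group and skin type is opened by a test of the covariate's association with the outcome. In the primary model a modifier with no average covariate effect reaches that check about 6% of the time, where a direct interaction test would find it about 78% of the time in adults and 47–50% in children. A modifier acting only in type 2-high participants reaches it about 69% and 42% of the time. A covariate with odds ratio 2 for severity and no modification reaches it about 74–76% and 45–48% of the time.

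The exact percentages rest on the 50/50 binary covariate, its independence from type 2 status, the unadjusted 0.05 trigger and the chosen effect sizes. The mismatch itself does not, since a main-effect test is not designed to detect an interaction. The rule in 9.2.1 and 9.2.2 has the same logical fault, of unmeasured size. The change is worth making because it is cheap, but the primary result does not depend on it.

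**What to change.** Delete the significance trigger from SAP 8.2, 9.1.1, 9.2.1 and 9.2.2, and align protocol 13.1. The sponsor should name in advance a short list of candidate modifiers. For each, fit the interaction whatever the covariate's main-effect p-value:

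- Primary objective: type 2 × covariate. Section 9.1.1 currently words this as "we may also fit a single model that includes the covariate and disease group with covariate interaction terms", but disease group is the outcome there, so the term should be restated.
- SO1: disease group × covariate.
- SO2: visit × outcome group × covariate.

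Keep continuous covariates continuous. Report the ratio of effects with its confidence interval and Benjamini-Hochberg adjustment, and state the family of tests. Show stratum estimates as description only, and claim a difference only on the interaction.

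The cost is SAP wording and a modest set of pre-specified models, with no new data. The downside is imprecision, especially in children, where the interaction test misses about half of the modification modelled in settings A and C. A wide confidence interval shows that limit openly.

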9.2 Primary Analysis of Secondary Endpoints/Outcomes

9.2.1 *Determining how gene expression in the skin (skin tape) differs between non-AD participants and those with current mild or moderate-to-severe AD disease [SO #1]*

This analysis will utilize WTS data from non-lesional and lesional skin tape samples collected at the Day 7 and End of Study Assessment (Day 168-224) Visits. To investigate whether skin gene expression differs due to AD status and severity of disease at each time point, we will carry out single-gene differential expression (DE) analysis using negative-binomial generalized linear models (GLM) to compare expression between

participants in different disease severity groups (non-AD, mild AD, and moderate-to-severe AD), while accounting for covariates. To assess effects of AD status, we will compare AD vs. non-AD, mild AD vs. non-AD, and moderate-to-severe AD vs. non-AD. We will compare mild AD vs. moderate-to-severe AD to explicitly test for differences based on AD severity. For all comparisons above and throughout this SAP, the Benjamini-Hochberg (BH) method will be used to adjust p-values to control the false discovery rate (FDR) at 5%, which we will apply across all tests that fall under a specific hypothesis (e.g., when testing whether gene expression is associated with non-AD vs AD, we will apply an adjustment for all genes tested. A separate adjustment will be applied when testing whether gene expression is associated with mild vs moderate-to-severe AD.

Although the above analyses will focus on non-lesional skin samples, which will be available for all participants, we will also examine differences in disease signatures between lesional and non-lesional skin in participants from whom we have both types of samples (AD participants only) using a linear mixed model. Variance stabilizing transformation (VST)-normalized gene expression (Love et al. 2014) will be used as the outcome and models will include fixed effects for skin type (lesional or non-lesional), disease severity (mild or moderate-to-severe), and skin type x disease severity interaction, along with a random intercept for each participant to account for pairing of lesional and non-lesional samples. The interaction term will allow us to explicitly test for different changes between mild and moderate-to-severe AD in lesional vs. non-lesional skin. Using this model, we will also be able to compare gene expression differences between disease groups within lesional skin. Note that each of the above models will be fit for each visit separately. The above models will also be fit separately for children and adults, after which we will fit a combined model using interaction terms with age group to identify severity changes that are shared and unique to age groups.

In total, there will be 22 distinct models:

Response	Population	Regressors	Model #
Single-gene differential expression from Non-lesional STS collected at Day 7	Adults (18+ year olds)	Non-AD vs. DNAD (all severity) at Day 7	1
		Non-AD vs Mild DNAD at Day 7	2*
		Non-AD vs Moderate-to-Severe DNAD at Day 7	3*
		Mild vs. Moderate-to-Severe DNAD at Day 7	4
	Children (6-17 year olds)	Non-AD vs. DNAD (all severity) at Day 7	5
		Non-AD vs Mild DNAD at Day 7	6*
		Non-AD vs Moderate-to-Severe DNAD at Day 7	7*
		Mild vs. Moderate-to-Severe DNAD at Day 7	8
Single-gene differential expression from Non-lesional STS collected at End of Study (Day 168-224)	Adults (18+ year olds)	Non-AD vs. DNAD (all severity) at End of Study	9
		Non-AD vs Mild DNAD at End of Study	10*
		Non-AD vs Moderate-to-Severe DNAD at End of Study	11*
		Mild vs. Moderate-to-Severe DNAD at End of Study	12
	Children (6-17 year olds)	Non-AD vs. DNAD (all severity) at End of Study	13
		Non-AD vs Mild DNAD at End of Study	14*
		Non-AD vs Moderate-to-Severe DNAD at End of Study	15*
		Mild vs. Moderate-to-Severe DNAD at End of Study	16

Single-gene differential expression from matching set of Non-lesional AND Lesional STS collected at Day 7	Adults (18+ year olds)	Mild vs. Moderate-to-Severe DNAD at Day 7, Non-lesional vs Lesional, Interaction	17
	Children (6-17 year olds)	Mild vs. Moderate-to-Severe DNAD at Day 7, Non-lesional vs Lesional, Interaction	18
	Adults AND Children	Mild vs. Moderate-to-Severe DNAD at Day 7, Non-lesional vs Lesional, Adults vs. Children, Interactions	19
Single-gene differential expression from matching set of Non-lesional AND Lesional STS collected at End of Study (Day 168-224)	Adults (18+ year olds)	Mild vs. Moderate-to-Severe DNAD at End of Study, Non-lesional vs Lesional, Interaction	20
	Children (6-17 year olds)	Mild vs. Moderate-to-Severe DNAD at End of Study, Non-lesional vs Lesional, Interaction	21
	Adults AND Children	Mild vs. Moderate-to-Severe DNAD at End of Study, Non-lesional vs Lesional, Adults vs. Children, Interactions	22

** Models 2,3,6,7,10,11,14, and 15 will evaluate the first of our secondary estimands that will directly answer the first of our secondary objectives. The remaining models serve as supportive analyses.*

The 22 models defined above will then be repeated with additional covariates as described in Section 8.2. If a covariate is found to be statistically significant in the model and if deemed appropriate, we will carry out sensitivity analyses by repeating analysis in participants stratified into covariate-based groups to determine whether effects qualitatively differ among stratified groups. For continuous covariates, this will require discretization. If sufficient samples are available for covariate-based groups, we may also fit a single model that includes the covariate and disease group x covariate interaction terms, enabling us to quantitatively determine whether disease effects differ by the covariate.

Pathway and enrichment analyses will be performed on differentially expressed gene (DEG) sets to determine the biological mechanisms that underlie transcriptional differences.

9.2.2 Determining how gene expression in the skin (skin tape) changes with standard-of-care treatment (two timepoints) among the study outcome groups: (1) topical steroid responders, (2) dupilumab responders, (3) dupilumab non-responders, (4) non-AD, and (5) long-term dupilumab responders [SO #2]

To investigate changes in skin gene expression due to standard-of-care treatment as delineated in the protocol and how these changes may differ with study outcome groups (i.e., groups based on treatment regimen and response), we will model gene expression at both Day 7 and End of Study (Day 168-224) Visits using linear mixed models. Gene expression data will be normalized using the VST method. Models will include fixed effect variables for visit, study outcome group (topical steroid responders, dupilumab-naïve responders, dupilumab-naïve non-responders, non-AD, and long-term dupilumab participants), and visit x

study outcome group interaction, along with relevant covariates and a random intercept for each participant to account for pairing of Day 7 and End of Study samples. Among the covariates, there will be a binary variable that further distinguishes topical steroid responders who had mild AD to begin with since baseline (set covariate = 1) versus those who actually improved from having moderate-to-severe AD at baseline (set covariate = 0) in order to consider them as “true” topical steroid responders to compare with among the other outcome groups in the model (all remaining groups would set covariate = 0 as well). Using this model, we will examine responses to standard-of-care treatment as delineated in the protocol by contrasting Day 7 and End of Study Assessment Visits within outcome groups. We will also examine differences in response to standard-of-care treatment between any two outcome groups by testing the interaction term for visit effect in one outcome group versus another.

As noted in Section 9.2.1, these analyses will focus on non-lesional skin samples. However, for each outcome group separately, we will also examine differences in response to standard-of-care treatment between lesional and non-lesional skin in participants from whom we have both types of samples (AD participants only) by fitting mixed models based on VST-normalized data that include a random intercept for each participant and fixed effect terms for skin type (lesional or non-lesional), visit, and skin type x visit interaction. Using these models, we will also be able to investigate gene expression responses to standard-of-care treatment for each outcome group within lesional skin. Note that for lesional skin, we will compare target skin sampled at End of Study that corresponds to the original lesional skin sampled in the target area at Day 7, even if the lesion has resolved over the course of treatment.

The above tests will be performed separately for children and adults. We will also fit a combined model, using interaction terms with age group, to identify changes with outcome group that are shared and unique to age groups.

In total, there will be 34 models:

Response	Population	Regression Analysis Group(s)	Group Comparisons	Model #
VST-normalized gene expression from Non-lesional STS collected at BOTH Day 7 AND End of Study	Adults	Topical Steroid Responders, Dupilumab Responders, Dupilumab Non-Responders, Non-AD, and Long-Term Dupilumab Responders	For the 5 analysis groups, Day 7 vs. End of Study Indicator, Interactions	1*
		
 1. Non-AD vs. Topical Steroid Responders 2. Non-AD vs. Dupilumab Responders 3. Non-AD vs. Dupilumab Non-Responders 4. Non-AD vs. Long-Term Dupilumab Responders 5. Topical Steroid Responders vs. Dupilumab Responders 6. Topical Steroid Responders vs. Dupilumab Non-Responders 7. Topical Steroid Responders vs. 	Between the select 2 groups, Day 7 vs. End of Study Indicator, Interaction	2-11

		Long-Term Dupilumab Responders 8. Dupilumab Responders vs. Dupilumab Non-Responders 9. Dupilumab Responders vs. Long-Term Dupilumab Responders 10. Dupilumab Non-Responders vs. Long-Term Dupilumab Responders		
	Children	Topical Steroid Responders, Dupilumab Responders, Dupilumab Non-Responders, Non-AD, and Long-term Dupilumab Responders	For the 5 outcome groups, Day 7 vs. End of Study Indicator, Interactions	12*
		1. Non-AD vs. Topical Steroid Responders 2. Non-AD vs. Dupilumab Responders 3. Non-AD vs. Dupilumab Non-Responders 4. Non-AD vs. Long-Term Dupilumab Responders 5. Topical Steroid Responders vs. Dupilumab Responders 6. Topical Steroid Responders vs. Dupilumab Non-Responders 7. Topical Steroid Responders vs. Long-Term Dupilumab Responders 8. Dupilumab Responders vs. Dupilumab Non-Responders 9. Dupilumab Responders vs. Long-Term Dupilumab Responders 10. Dupilumab Non-Responders vs. Long-Term Dupilumab Responders	Between the select 2 outcome groups, Day 7 vs. End of Study Indicator, Interaction	13-22
VST-normalized gene expression from matching set of Non-lesional AND Lesional STS collected at BOTH Day 7 AND End of Study (for the same target area on the lesional skin)	Adults	Topical Steroid Responders	Non-lesional vs Lesional Indicator, Day 7 vs. End of Study Indicator, Interaction	23
		Dupilumab Responders	Non-lesional vs Lesional Indicator, Day 7 vs. End of Study Indicator, Interaction	24
		Dupilumab Non-Responders	Non-lesional vs Lesional Indicator, Day 7 vs. End of Study Indicator, Interaction	25
		Long-term Dupilumab Responders	Non-lesional vs Lesional Indicator, Day 7 vs. End of Study Indicator, Interaction	26
	Children	Topical Steroid Responders	Non-lesional vs Lesional Indicator, Day 7 vs. End of Study Indicator, Interaction	27
		Dupilumab Responders	Non-lesional vs Lesional Indicator, Day 7 vs. End of Study Indicator, Interaction	28
		Dupilumab Non-Responders	Non-lesional vs Lesional Indicator, Day 7 vs. End of Study Indicator,	29

			Interaction	
		Long-term Dupilumab Responders	Non-lesional vs Lesional Indicator, Day 7 vs. End of Study Indicator, Interaction	30
	Adults AND Children	Topical Steroid Responders	Non-lesional vs Lesional Indicator, Day 7 vs. End of Study Indicator, Adults vs. Children Indicator, Interactions	31
		Dupilumab Responders	Non-lesional vs Lesional Indicator, Day 7 vs. End of Study Indicator, Adults vs. Children Indicator, Interactions	32
		Dupilumab Non-Responders	Non-lesional vs Lesional Indicator, Day 7 vs. End of Study Indicator, Adults vs. Children Indicator, Interactions	33
		Long-term Dupilumab Responders	Non-lesional vs Lesional Indicator, Day 7 vs. End of Study Indicator, Adults vs. Children Indicator, Interactions	34

** Models 1 and 12 will evaluate the second of our secondary estimands that will directly answer the second of our secondary objectives. The remaining models serve as supportive analyses.*

The 34 models defined above will then be repeated with additional covariates as described in Section 8.2. If a covariate is found to be statistically significant in the model and if deemed appropriate, we will carry out sensitivity analyses by repeating analysis in participants stratified into covariate-based groups to determine whether effects qualitatively differ among stratified groups. For continuous covariates, this will require discretization. If sufficient samples are available for covariate-based groups, we may also fit a single model that includes the covariate and disease group with covariate interaction terms, enabling us to quantitatively determine whether disease effects differ by the covariate.

Pathway and enrichment analyses will be performed on DEG sets.

